8.3.3.3 EXPECTEDNESS

The safety officer in conjunction with the PI will determine if an AE is expected or unexpected. An AE will be considered unexpected if the nature, severity, or frequency of the event is not consistent with the risk information previously described for the study procedures.

8.3.4 TIME PERIOD AND FREQUENCY FOR EVENT ASSESSMENT AND FOLLOW-UP

All adverse events that are both serious and unexpected will be reported by the pilot PI and the Roybal Center PI to the IRB's, NIA PO and to the Safety Officer, within 48 hours of the study's knowledge of SAE. The summary of all other SAEs will be reported to NIA PO and to the Safety Officer, quarterly, unless otherwise requested by the Safety Officer.

8.3.5 ADVERSE EVENT REPORTING

Adverse events will be reported by the PI of the Pilot project to the PI of the Roybal Center and the head of the IRB at Northeastern. The Roybal Center PI will report the problems or events to the head of the IRB at Brandeis University and the NIA Program Officer, and the Safety Officer within 48 h by fax or email according to the Northeastern's IRB written guidelines for interventional studies. All adverse events that are both serious and unexpected (i.e., that have not been previously reported for the study's intervention) will be reported by the pilot PI and the Roybal Center PI to the IRB's, NIA PO and to the Safety Officer, within 48 hours of the study's knowledge of SAE. The summary of all other SAEs will be reported to NIA PO and to the Safety Officer, quarterly, unless otherwise requested by the Safety Officer. All deaths in greater than minimal risk studies require expedited reporting (usually within 24 hours of study's knowledge of death). The report of death will be submitted to NIA Program Officer and to the Safety Officer and the institutional IRB's by the pilot PI and/or the Roybal Center PI.

8.3.6 SERIOUS ADVERSE EVENT REPORTING

See section 8.3.5

8.3.7 REPORTING EVENTS TO PARTICIPANTS

NA

8.3.8 EVENTS OF SPECIAL INTEREST

NA

8.3.9 REPORTING OF PREGNANCY

NA

8.4 UNANTICIPATED PROBLEMS

8.4.1 DEFINITION OF UNANTICIPATED PROBLEMS

Unanticipated problems are those that:

- Are unexpected in terms of nature, severity, or frequency, given (a) the research procedures that are described in the protocol-related documents and (b) the characteristics of the study population;
- Are related or possibly related to participation in the research suggest that the research places participants and others at greater risk of harm than was previously known or recognized

8.4.2 UNANTICIPATED PROBLEMS REPORTING

See section 8.3.5.

8.4.3 REPORTING UNANTICIPATED PROBLEMS TO PARTICIPANTS

NA

9 STATISTICAL CONSIDERATIONS

9.1 STATISTICAL HYPOTHESES

- Primary Endpoint(s): Daily total and bouts of physical.

The treatment group using Companion will show greater improvements in daily activity and sedentary behavior outcomes than controls after 16 and 24 weeks. Alternatively, our null hypothesis is that there will be no difference in the treatment group for daily activity and sedentary behavior outcomes after 16 and 24 weeks.

9.2 SAMPLE SIZE DETERMINATION

Sample size is based on change in HbA1C after 16 weeks of training in adults >60 y (n=22). We used a health outcome variable to compute sample size to examine the translational effect of behavior change due to Companion on the health of adults >60 y. In our data, partial η^2 (effect size) for the interaction effect between group and time (pre – 16 week) equaled 0.5 corresponding to a medium effect size. With alpha of .01, power of 0.85, two groups, 3 repeated assessments, and an estimated inter-correlation between assessments of 0.5, the required sample is 39; we will recruit 46 participants. Hypothesis testing for all outcomes will entail an intent-to-treat two-tailed design with a type I error of 0.05.

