9.4.2 ANALYSIS OF THE PRIMARY ENDPOINT(S)

The primary endpoint will be summarized from body-worn sensor data and is a continuous variable. Hypothesis testing entailed an intent-to-treat two-tailed design with a nominal type I error of 0.05. Random intercept mixed linear models that account for repeated measures will be used to analyze the primary outcome. Models will be adjusted for covariates and the baseline value of the outcome variable where necessary. Post-hoc pairwise comparisons for primary outcomes will be adjusted for multiple testing using Bonferroni corrections. Results will be presented as Least-squares means (LSMEANS) with 95% confidence intervals. Effect sizes and confidence intervals will be calculated for all comparisons.^{23,24} Additionally, we will conduct sensitivity analyses where missing outcome data attributable to random factors will be imputed using joint multiple imputation and analyzed using mixed linear modelling adjusted for covariates.^{25,26}

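### Section 9.2: partial eta-squared 0.5 is not a medium effect, the required sample of 39 does not follow from the interaction described, and no primary accelerometry outcome has a stated power or detectable difference

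*Combined protocol and SAP*

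**What the plan says.** Section 9.2 takes its effect from the investigators' own earlier data: "Sample size is based on change in HbA1C after 16 weeks of training in adults >60 y (n=22"). The effect is the "interaction effect between group and time (pre – 16 week"), and partial eta-squared for it "equaled 0.5 corresponding to a medium effect size. With alpha of .01, power of 0.85, two groups, 3 repeated assessments". With a correlation of 0.5 between assessments the section arrives at 39 required and 46 recruited.

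The section gives its reason for using HbA1c: "We used a health outcome variable to compute sample size to examine the translational effect of behavior change due to Companion". HbA1c is an exploratory endpoint in the synopsis, section 3 and section 6.1.1. The primary outcomes are accelerometry durations and bout counts.

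The paragraph ends: "Hypothesis testing for all outcomes will entail an intent-to-treat two-tailed design with a type I error of 0.05". Section 9.1 states the primary hypothesis: "The treatment group using Companion will show greater improvements in daily activity and sedentary behavior outcomes than controls after 16 and 24 weeks". For the analysis, section 9.4.2 says: "Random intercept mixed linear models that account for repeated measures will be used to analyze the primary outcome". It adds: "Results will be presented as Least-squares means (LSMEANS) with 95% confidence intervals".

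**The concern.** This paragraph is the only prospective power statement in the document. A reader relies on it to know what test was powered, for what effect, and what 46 participants can detect. Three things prevent that.

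- The number 0.5 and the label medium cannot both be right on the partial eta-squared scale, so the planned effect is unknown.
- The figure 39 should be the smallest sample giving 85% power for the interaction named, and it needs to be checked against that test.
- The 85% refers to an exploratory endpoint. Nothing equivalent is given for the primary outcomes, so no one can say beforehand what size of behavioural difference the trial could detect.

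**Working it through.** **Inputs.** From section 9.2: alpha .01, power 0.85, two groups, m = 3 assessments, correlation ρ = 0.5, partial eta-squared 0.5, required N = 39. Allocation is 1:1 (section 6.3). The effect-size benchmarks are the usual conventions and are not in the document. Sphericity is assumed.

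**Step 1: the effect size.** f = √(η²/(1 − η²)) = √(0.5/0.5) = 1.0. A conventional medium effect is f = 0.25, for which η² = 0.0625/1.0625 ≈ 0.06. The value 0.5 is called medium only as Cohen's d; even f = 0.5 is large.

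**Step 2: reproducing 39.** The stated alpha, power, groups, assessments and correlation give exactly 39 for a between-group main effect with 0.5 entered as f. There λ = f²·N·m/(1 + (m − 1)ρ), with 1 and N − 2 degrees of freedom.

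- N = 38: λ = 0.25 × 38 × 3/2 = 14.25, power 0.847.
- N = 39: λ = 0.25 × 39 × 3/2 = 14.625, power 0.859.

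This test compares the groups averaged over all assessments, including baseline, where randomised groups should differ only by chance. It is not a difference in improvement.

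**Step 3: the interaction described.** Degrees of freedom are m − 1 and (N − 2)(m − 1). There are two conventions for the noncentrality:

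- A, correlation supplied separately: λ = f²·N·m/(1 − ρ).
- B, eta-squared taken from ANOVA output and so already reflecting the correlation: λ = f²·(N − 2)(m − 1).

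| Effect | A: minimum N | λ at that N | B: minimum N | λ at that N |
|---|---|---|---|---|
| f = 1.0 (η² = 0.5) | 6 | 1 × 6 × 3/0.5 = 36 | 12 | 1 × 10 × 2 = 20 |
| f = 0.5 | 13 | 0.25 × 13 × 3/0.5 = 19.5 | 36 | 0.25 × 34 × 2 = 17 |
| f = 0.25 | 44 | 0.0625 × 44 × 3/0.5 = 16.5 | 128 | 0.0625 × 126 × 2 = 15.75 |

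None is 39. The quoted effect covers two time points; with m = 2 at alpha .01 the figures are 8, 17 and 56 (A) or 19, 58 and 215 (B), again not 39. Near matches of 38 (A, f = 0.25) and 40 (B, f = 0.5) need both m = 2 and alpha .05, against the stated inputs.

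**Step 4: does this show a shortfall?** If f = 0.25 was meant, N = 46 with three assessments gives power 0.876 at alpha .01 and 0.964 at .05 under A, but 0.289 and 0.530 under B. At f = 1.0 either convention needs far fewer than 39. The text does not say which case applies.

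**Step 5: what 46 can detect in a primary outcome.** The document gives no SD, so results are in SD units. Assumptions: one outcome, one follow-up, two-sided .05, 85% power, no multiplicity adjustment.

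- Unadjusted, noncentral t with noncentrality d·√(n₁n₂/(n₁ + n₂)): 23 per arm needs d ≈ 0.90; 20 and 19 analysed needs d ≈ 0.99.
- Baseline-adjusted: the SD shrinks by √(1 − ρ²). At ρ = 0.5, 0.903 × 0.866 = 0.78. Allowing for chance baseline imbalance and one further degree of freedom gives 0.79. At ρ = 0.3 it is 0.87 and at ρ = 0.7 it is 0.65. With 20 and 19 analysed at ρ = 0.5 it is 0.87.
- Alpha halved for two follow-ups, baseline-adjusted, ρ = 0.5: 0.87.
- Bonferroni over six variables (duration and bout count for light activity, moderate-to-vigorous activity and sedentary behaviour; alpha 0.05/6 = 0.0083): 1.13 unadjusted, 0.99 baseline-adjusted at ρ = 0.5.
- Average of both follow-ups, baseline-adjusted, ρ = 0.5: 0.65.

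**The case against.** The strongest reply is that nothing in the conduct of the trial depends on this. It is a single-site Phase 1A study. At the effect literally stated, 39 is far more than enough. Read as f = 0.5 from ANOVA output, the interaction needs 36, and 39 gives 90% power at alpha .01. Read as f = 0.25 under convention A, 46 gives 88%. The HbA1c choice is declared and explained. The only behavioural pilot figure is a fall in sitting of about 2.1 h/day in six people, without an SD (section 2.2), so a primary-outcome calculation had little to rest on. Section 9.4.2 commits to effect sizes and confidence intervals, which will show what a null result rules out.

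Most of this stands, and it limits the severity. Two lesser points also shrink. Sizing at .01 and testing at .05 is conservative, since the .05 tests have more power than claimed; it needs one line of explanation and is not an error. Applying a pre-to-16-week effect to three assessments is an undeclared assumption, and the n = 22 data needed to judge it are not in the document.

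What the reply does not remove is that section 9.2 makes a formal 85% power claim that does not follow from the test it names. Confidence intervals after the trial do not correct that.

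**Conclusion.** Wrong as written; it should be fixed. The effect-size label is wrong by algebra. The 39 is not the required sample for the described interaction under either convention at f = 1.0, 0.5 or 0.25. No primary accelerometry outcome has a power, SD or detectable difference.

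Two stronger readings are tempting and not supported. A reader might infer that the trial is underpowered. That requires taking the word medium as right, the 0.5 as wrong, and convention B as the one used, and the document settles none of these. It shows neither adequacy nor shortfall. A reader might also infer that the sponsor ran a between-group test by mistake. The exact match at 39 makes this plausible, but the inputs used are not shown, so it remains an inference.

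The interaction figures rest on sphericity and on the stated correlation of 0.5. The detectable differences rest on complete data for the numbers analysed. The baseline-adjusted ones also assume a correlation that the document does not support for accelerometry, and sections 9.4.1 and 9.4.2 make baseline adjustment conditional.

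**What to change.** Keep N = 46 and the HbA1c rationale. In section 9.2:

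1. Correct the effect-size metric and its label.
2. Name the test and the alpha used for sizing, with one line on why it is stricter than the testing alpha. Declare as an assumption that a two-time-point effect is applied to three assessments.
3. Give inputs that reproduce 39 for the named test, or withdraw the 39 and the 85% claim.
4. Add a detectable difference for one named primary accelerometry outcome, with its assumptions. For example:

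> With 46 analysed (23 per arm), two-sided 0.05, one outcome at one follow-up and no multiplicity adjustment, 85% power requires about 0.90 SD without baseline adjustment, or about 0.79 SD with baseline adjustment at an assumed correlation of 0.5 (0.87 SD at 0.3, 0.65 SD at 0.7); with 39 analysed, about 0.99 SD or, at correlation 0.5, 0.87 SD.

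If alpha is to be split over the two follow-ups or over six primary variables, state the corresponding figure from the last step of the working instead. Quote the 0.65 SD for the average of both follow-ups only if that contrast is named as primary.

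The cost is rewriting one section, with no added participants, visits or analyses. The sponsor must choose the outcome and contrast to which the statement applies, and the stated figure will look less favourable.

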9.3 POPULATIONS FOR ANALYSES

Intention-to-Treat (ITT) Analysis Population (i.e., all randomized participants)

9.4 STATISTICAL ANALYSES

9.4.1 GENERAL APPROACH

Descriptive statistics, for all normally distributed continuous data will be presented as means with standard deviations. Hypothesis testing will entail an intent-to-treat two-tailed design with a nominal type I error of 0.05. All participants will be included in the intent-to-treat analyses according to randomization regardless of their subsequent status. Missing data due to losses to follow-up will be

assumed to be at random. Random intercept mixed linear models that account for repeated measures will be used to compare primary and exploratory outcomes measured at various timepoints during the study. Models will be adjusted for covariates and the baseline value of the outcome variable where necessary.

9.4.2 ANALYSIS OF THE PRIMARY ENDPOINT(S)

The primary endpoint will be summarized from body-worn sensor data and is a continuous variable. Hypothesis testing entailed an intent-to-treat two-tailed design with a nominal type I error of 0.05. Random intercept mixed linear models that account for repeated measures will be used to analyze the primary outcome. Models will be adjusted for covariates and the baseline value of the outcome variable where necessary. Post-hoc pairwise comparisons for primary outcomes will be adjusted for multiple testing using Bonferroni corrections. Results will be presented as Least-squares means (LSMEANS) with 95% confidence intervals. Effect sizes and confidence intervals will be calculated for all comparisons.^{23,24} Additionally, we will conduct sensitivity analyses where missing outcome data attributable to random factors will be imputed using joint multiple imputation and analyzed using mixed linear modelling adjusted for covariates.^{25,26}

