Control Group: This group will not receive the Companion, which will be the only difference with the treatment group. I.e., the control group will receive standard treatment– the supervised training program and an exercise prescription for those days when they are on their own. This will be done on the two days when control group participants meet face-to-face with the trainer for supervised training.

Primary Outcomes: Total duration and number of bouts of: (i) light and moderate-to-vigorous physical activity and (ii) sedentary behavior measured over a period of one week using accelerometry.^{38,39} Week-long measures will be made at baseline, and weeks 16 and 24.

Exploratory Outcomes: Cardiometabolic health: Plasma glucose, HbA1C, insulin, and lipids. Body composition: lean and fat mass. Physical function. Muscular and aerobic fitness. Cognition.⁴² Perceptions of competence related to health behaviors. Autonomy support (from companion). Autonomous motivation (for physical activity). Relatedness (to the Companion). General satisfaction.

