Participants in the lifestyle physical activity intervention group will also have the battery life of his or her wrist-worn activity monitor frequently monitored by the researchers via the passive data transfer system. When the researchers detect that the device has a low battery (battery life is approximately 2-3 weeks), the participant will be prompted to schedule a time to receive a new device from the researchers. The researcher will go to the participant's office or home to collect the monitor and return it charged by the next day to commence the daily physical activity measurement.

We will encourage participants in both groups to wear the sensors as much as possible so that: 1) we may be able to understand the differences in daily/weekly physical behavior change effects between the two intervention approaches, and 2) we may be able to tailor daily recommendations of participants in the lifestyle physical activity intervention group to maximize and maintain his or her gains and to help meet his or her goals. Participants may remove the sensors for brief intervals throughout the day (e.g., for showering). The researchers may provide participants in the lifestyle physical activity intervention group with retrospective feedback of his or her physical activity measurements via text-message frequently (4 to 7 times a day at intervals of 1 to 4 hours between 7

am – 10 pm), following the virtual session (Table 1 #8). To reiterate, daily retrospective feedback (health coaching) will last for 4 months, concluding at the month-4 follow up.

Change in outcome measurements will be provided to participants after the follow up at month 6, when requested by the participant.

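### The random-intercept-only model assumes equal variances, and possibly one common correlation, at visits that straddle the end of coaching, so the week-24 standard error may be too small or too large

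*Combined protocol and SAP*

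**What the plan says.** Section 9.4.1 applies one model to everything: "Random intercept mixed linear models that account for repeated measures will be used to compare primary and exploratory outcomes". Section 9.4.2 repeats this for the primary endpoint ("Random intercept mixed linear models that account for repeated measures will be used to analyze the primary outcome"), and 9.4.9 repeats it for the exploratory ones. None of these sections names a residual covariance structure, a random slope, a robust standard error or a degrees-of-freedom method. The one planned sensitivity analysis, multiple imputation, concerns missing data and does not vary the covariance.

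On baseline, 9.4.2 says "Models will be adjusted for covariates and the baseline value of the outcome variable where necessary". This leaves open whether baseline is a covariate (two outcome rows per person) or an outcome row (three).

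Section 6.1.1 fixes the visits: "Week-long measures will be made at baseline, and weeks 16 and 24". Section 8.1 says that "daily retrospective feedback (health coaching) will last for 4 months, concluding at the month-4 follow up", and 6.1.1 limits supervised training to the first 16 weeks, so week 24 is off treatment. Both times carry the primary hypothesis in 9.1: "The treatment group using Companion will show greater improvements in daily activity and sedentary behavior outcomes than controls after 16 and 24 weeks". Section 9.4.2 sets a two-sided 5% level. The only correlation in the documents is in 9.2: "an estimated inter-correlation between assessments of 0.5".

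**The concern.** A random intercept with independent residuals gives every visit the same variance and every pair of visits the same correlation. Here the intervals are unequal and treatment ends between the second and third visits, so neither assumption is safe. If baseline and week 24 are the least correlated pair, a pooled correlation understates the variance of the week-24 change. If week 24 resembles baseline more than week 16 does, the pooled value overstates it. Unequal variances have similar effects, and they matter even when baseline is a covariate.

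The week-24 comparison carries the part of the primary objective about sustained change. Its p-value and its 95% confidence interval would be miscalibrated together. The Bonferroni adjustment in 9.4.2 does not help, because it acts on p-values already computed from that standard error. Missing data add a further reason for care: 9.4.1 assumes missingness at random, likelihood estimates then lean on the covariance model, and 4.4 counts a participant as complete after the 4-month visit, so gaps at week 24 are foreseeable.

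**Working it through.** **Inputs.** From the documents: 46 participants allocated 1:1, so 23 per arm if the split is even; three visits; two-sided 5%; one correlation of 0.5. Assumed: every other correlation and SD below, complete data, and no true effect. Correlations are listed as baseline-week 16 / week 16-week 24 / baseline-week 24.

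**1. The plan's own figure.** Section 9.2 requires 39 participants. This is reproduced by a between-group repeated-measures test with f = 0.5, alpha 0.01, m = 3 and rho = 0.5. The noncentrality is f² × N × m / [1 + (m − 1) × rho] = 0.25 × 39 × 3 / 2 = 14.6, giving power 0.859 at N = 39 and 0.847 at N = 38, against a target of 0.85. That calculation also assumes one common correlation. (The wording in 9.2 describes an interaction and a partial eta-squared, which does not give 39. That is a separate matter.)

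**2. Baseline as an outcome row.** The contrast is the group difference in change from baseline to week 24. The random-intercept variance uses 2 × (mean variance − mean covariance). The true variance uses v0 + v24 − 2 × c(0,24). With unit variances the ratio of modelled to true standard error is

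sqrt[(1 − mean r) / (1 − r(0,24))].

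- 0.5/0.5/0.5: sqrt(0.5 / 0.5) = 1.00
- 0.6/0.7/0.5: sqrt(0.4 / 0.5) = 0.89
- 0.6/0.7/0.4: sqrt(0.433 / 0.6) = 0.85
- 0.4/0.5/0.6: sqrt(0.5 / 0.4) = 1.12
- 0.5 throughout, SD 1.3 at week 16 only: mean variance (1 + 1.69 + 1) / 3 = 1.23; mean covariance (0.65 + 0.65 + 0.5) / 3 = 0.60; sqrt(2 × 0.63 / 1) = 1.12

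**3. Baseline as a covariate.** There are two outcome rows and one correlation, so the remaining restriction is equal residual variance at weeks 16 and 24. With unit variances the residual variances are 1 − r(0,16)² and 1 − r(0,24)², and the ratio is sqrt(their mean / the week-24 value).

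- 0.5/0.5/0.5: 0.75 and 0.75; ratio 1.00
- 0.6/0.7/0.5: 0.64 and 0.75; sqrt(0.695 / 0.75) = 0.96
- 0.6/0.7/0.4: 0.64 and 0.84; sqrt(0.74 / 0.84) = 0.94
- 0.4/0.5/0.6: 0.84 and 0.64; sqrt(0.74 / 0.64) = 1.08
- SD 1.3 at week 16 only: 1.69 × 0.75 = 1.27 and 0.75; sqrt(1.01 / 0.75) = 1.16

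**4. Simulated week-24 type I error with the random-intercept model, nominal 5%** (20,000 to 100,000 trials per scenario).

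| Assumed pattern | Outcome row | Covariate |
|---|---|---|
| 0.5/0.5/0.5 | 5% | 5% |
| 0.6/0.7/0.5 | about 8% | about 6% |
| 0.6/0.7/0.4 | about 9.5% | about 6.5% to 7% |
| 0.4/0.5/0.6 | about 3% | about 3.5% |
| 0.5 throughout, SD 1.3 at week 16 only | about 2.8% | about 2.3% to 2.5% |
| 0.5 throughout, SD 1.3 at week 24 only | about 6% | about 7.6% |

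With an unstructured covariance the error was between 4.8% and 5.3% in every scenario tried, under either reading of baseline.

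**5. Price of the unstructured model.** With baseline as an outcome row and complete data, error degrees of freedom for the week-24 contrast go from 2 × (46 − 2) = 88 to 46 − 2 = 44. The two-sided 5% critical value rises from 1.987 to 2.015, so intervals are about 1.4% wider for the same standard error (2.015 / 1.987 = 1.014).

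**The case against.** A random-intercept model is a conventional choice for a small, three-visit, early-phase trial, and the phrase does not strictly rule out an added residual structure. The one documented correlation, 0.5 with equal variances, produces no error at all. Halving the degrees of freedom is a real cost, and with dropout a richer covariance may fail to converge. These points stand. They limit the size of the concern but do not remove it: no other structure is written down, and the 0.5 belongs to a sample size based on HbA1C rather than on the accelerometer outcomes.

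A reader might infer two stronger things. The first is that the week-24 error rate will be inflated. The documents do not support that. They give no visit-specific correlations or SDs for the primary outcomes. Once coaching and supervised sessions stop, behaviour could also drift back towards baseline, which is a pattern that could make the test conservative.

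The second is that the model must force one correlation on all three visits. That is so only if baseline is an outcome row. Section 9.4.2 equally allows baseline as a covariate, and more than half of the excess error under the two decaying-correlation patterns then disappears.

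**Conclusion.** The point holds in a conditional, two-sided form. As written, the model relies on equal variances, and on a common correlation if baseline is an outcome row, at visits where the end of treatment makes both doubtful. In the scenarios tried, week-24 type I error ranges from about 2.3% to about 9.5%, depending on the assumed covariance and on how baseline enters. It is 5% under the plan's own correlation with equal variances. All departures from 5% rest on assumed values, complete data and 23 per arm.

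The case for change does not depend on which pattern is true, because the unstructured covariance holds its level in all of them. The required sample of 39 is unaffected. This is a worthwhile refinement, not a threat to the trial's validity.

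One related inconsistency bears on visit spacing and should be reconciled: the schedule in 1.3 puts the third measurement at Day 240-250, whereas 6.1.1 puts it at week 24 (day 168) and 8.1 at month 6.

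**What to change.** In 9.4.1 and 9.4.2, and in 9.4.9 for consistency:

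- Replace the random-intercept-only model with an unstructured within-person covariance across visits and Kenward-Roger degrees of freedom.
- State whether baseline is a covariate or an outcome row. This decides which assumptions bind.
- Name a fallback for non-convergence: a random intercept with a small-sample-corrected robust standard error.

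The change is to wording only, with no added participants or visits. With baseline as an outcome row the covariance has 6 parameters instead of 2, so four more. With baseline as a covariate it has 3 instead of 2, so one more. The loss of error degrees of freedom costs little precision with complete data and somewhat more if dropout is heavy, which is why the fallback should be fixed in advance.

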1 PROTOCOL SUMMARY

1.1 SYNOPSIS

Title:	An Integrated Two-Way Communication and Near-Real-Time Sensing System to Detect and Modify Daily Inactivity among Adults Over Age 60
Grant Number:	5P30AG048785-07
Study Description:	The objective is to test if Companion, an Integrated Two-Way Communication and Near-Real-Time Sensing System, improves and sustains overall daily free-living activity and sedentary behavior in adults over 60 y. The central hypothesis is that Companion will improve overall daily free-living activity and sedentary behavior in adults >60 y and thereby improve their health.
Objectives*:	
Primary Objective: Determine if Companion improves free-living activity and sedentary behavior and sustains this change in adults >60y. In this RCT (n=46), both treatment and control groups will engage in a 16-week supervised exercise program and then be followed-up after 24 weeks.^{1,2} Companion will be deployed in the treatment group (n=23) only. Primary outcomes are daily total and bouts of physical activity and sedentary time.
 
Exploratory Objective: Explore if supplementing supervised exercise with Companion further improves and sustains cardiometabolic health, body composition, cognition, and psychosocial outcomes.

Endpoints*:	
Primary Endpoint: Physical activity and sedentary time: Daily total and bouts
 
Exploratory Endpoints: Anthropometrics; Plasma glucose; HbA1C; Insulin; Lipids; Lean and fat mass; Physical function; Muscular and aerobic fitness; Cognition; perceptions of competence related to health behavior; Autonomy support (from companion); Autonomous motivation (for physical activity); Relatedness (to the Companion); General satisfaction.

Study Population:	N= 46, gender- NA, age >60 y, demographic group- older adults; general health status- healthy; geographic location- Boston and surrounding neighborhoods.
Phase* or Stage:	1A
Description of Sites/Facilities Enrolling Participants:	The Human Performance and Exercise Science (HPES) Laboratory is located in the Behrakis Health Science Center at Northeastern University, which will be the sole site for the study. Participants who do not prefer to have their measurements conducted at their residence will come to the lab to have measurements completed. The study is not intended to include sites outside of the United States.

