6.3 MEASURES TO MINIMIZE BIAS: RANDOMIZATION AND BLINDING

1:1 Simple Randomization conducted by graduate assistant.

It has been suggested that blinding in behavioral interventions such as those involving physical activity and exercise is comparatively more challenging than in pharmacological or medical studies; this may be more relevant to pilot trials that are not conducted as part of a larger trial, which aim to assess the conceivable benefits of an intervention and the potential of conducting a future definitive RCT.⁷⁻⁹ While the health coaches and participants will not be blinded to treatment allocation, we minimize bias via the use of objectively measured outcome variables in both aims. Furthermore, the statistical analyst will be blinded to treatment allocation during analyses.

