9.4.5 BASELINE DESCRIPTIVE STATISTICS

The intervention and control group will be compared for differences in baseline characteristics using linear mixed models.

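### Sections 9.4.1 and 9.4.2 leave adjustment for the outcome's own baseline optional with no criterion, so the primary contrast may be reported with about a third more variance than needed and the model can be picked after the data are seen

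*Combined protocol and SAP*

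**What the plan says.** On the primary model, section 9.4.2 says "Random intercept mixed linear models that account for repeated measures will be used to analyze the primary outcome", and then "Models will be adjusted for covariates and the baseline value of the outcome variable where necessary". Section 9.4.1 repeats the second sentence for all outcomes. Neither section says when adjustment is necessary, who decides or at what stage, or which covariates are meant. Neither says whether the baseline measurement is one of the repeated outcomes or a covariate.

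Section 9.4.5, under baseline descriptive statistics, adds: "The intervention and control group will be compared for differences in baseline characteristics using linear mixed models". It gives that comparison no role in choosing the model.

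The setting is small and unstratified. The synopsis puts 23 participants in the treatment group ("Companion will be deployed in the treatment group (n=23) only"), section 9.2 recruits 46 in total ("the required sample is 39; we will recruit 46 participants"), and section 6.3 specifies "1:1 Simple Randomization conducted by graduate assistant". Section 6.1.1 schedules the primary accelerometer measures at baseline, week 16 and week 24. Section 9.4.2 tests at a two-sided 0.05 level.

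**The concern.** Whether to adjust for the outcome's own baseline should not depend on how balanced the arms look. If baseline predicts follow-up, adjusting gains precision in balanced and unbalanced samples alike, and it uses a measurement that is already scheduled for everyone. An optional rule puts two things at stake.

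- **Precision and the realised estimate.** An analysis that ignores baseline carries part of any chance imbalance into the reported effect. One that simply subtracts baseline over-corrects it.
- **Error control.** Section 6.1.1 lists total duration and number of bouts for light activity, moderate-to-vigorous activity and sedentary behavior. The adjustment choice can be made separately for each. If it is made with results in view, the nominal 0.05 no longer describes the procedure.

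**Working it through.** **Inputs.** From the documents: 23 per arm (synopsis), correlation r = 0.5 between assessments (section 9.2) and two-sided 0.05 (section 9.4.2). Assumed: outcome SD of 1 at each visit, complete data, one follow-up contrast, true effects of 0.5 and 0.8 SD, and r from 0.3 to 0.7. The 23/23 split is also an assumption, because simple randomization does not guarantee it. The plan gives no precision figure for a primary outcome. Its required sample of 39 comes from HbA1C and is not used here.

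**Step 1: variance of the contrast.** The follow-up-only variance is 2/23 = 0.087 (SE 0.295). The other analyses multiply it by a factor:

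- change from baseline: 2(1 - r) = 1.00 at r = 0.5, so 0.087;
- baseline-adjusted: 1 - r² = 0.75 at r = 0.5, so 0.065, or about 0.067 in simulation, where the slope is estimated.

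The reduction is 1 - 0.75 = 25% in theory and 1 - 0.067/0.087 = 23% in simulation. Seen from the other side, the unadjusted variance is 1/0.75 = 1.33 times the adjusted one. An unadjusted analysis of 46 people is worth 46 × 0.75 = 34.5 adjusted participants.

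**Step 2: power for an assumed 0.8-SD effect.** With the normal approximation, power = Φ(0.8/SE - 1.96). At r = 0.5, follow-up-only gives Φ(0.8/0.295 - 1.96) = 77%, and adjusted gives Φ(0.8/0.255 - 1.96) = 88%.

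| r | follow-up only | change | adjusted |
|---|---|---|---|
| 0.3 | 77% | 63% | 81% |
| 0.5 | 77% | 77% | 88% |
| 0.7 | 77% | 94% | 97% |

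Simulation with t-tests runs one or two points lower. At r = 0.5 it gives about 75-76% for follow-up-only, 76% for change and 86% adjusted. At r = 0.3 adjustment takes follow-up-only from 76% to 79%. At r = 0.7 it takes follow-up-only from 76% to 96%, and change from 93% to 96%. For a 0.5-SD effect at r = 0.5 the figures are 38% unadjusted and 47% adjusted.

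**Step 3: chance imbalance.** The baseline mean difference has SE 0.295, so P(|difference| ≥ 0.5 SD) = 2[1 - Φ(0.5/0.295)] = 0.09 for each outcome. Given an observed baseline difference δ, the expected shift in the estimate is rδ for follow-up-only, (r - 1)δ for change and 0 when adjusted. With δ = 0.5 and r = 0.5 these are +0.25, -0.25 and 0 SD. At r = 0.3 the first two are +0.15 and -0.35; at r = 0.7 they are +0.35 and -0.15.

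**Step 4: type I error under no effect.** In simulation at r = 0.5, the unadjusted and adjusted tests each reject in about 5% of trials. Reporting the smaller of those two p-values rejects in 7.1% (6-8% over r = 0.3 to 0.7). Reporting the smallest of adjusted, unadjusted and change rejects in 9.5% (9-10% over the range).

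**The case against.** Four points can fairly be made for the plan.

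1. **Baseline may already be in the model.** Section 9.2 counts three repeated assessments and takes its effect from a group-by-time interaction, and the hypotheses speak of improvements. On that reading baseline is a repeated outcome, and a further covariate might indeed be unnecessary. This stands as a possible reading, but section 9.4.2 does not state it. Nor does it remove the loss: an unconstrained group-by-time contrast behaves like a change score, with no variance gain over follow-up-only at r = 0.5 and with imbalance over-corrected. It does shrink the gain from adjustment to about 3 points at r = 0.7.
2. **The correlation is borrowed.** The 0.5 belongs to an HbA1C calculation, not to accelerometry. This stands, which is why a range is shown. At r = 0.3 the gain over follow-up-only is small.
3. **The analyst is blinded (section 6.3).** That limits steering toward a favoured arm. It does not hide p-values or prevent a choice between models.
4. **Chance imbalance is not bias.** Averaged over randomizations, all three estimators are unbiased. The shifts in step 3 concern the one trial that is run.

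A reader might also infer that the section 9.4.5 comparison is what decides necessity, and object that such a test has only 38% power (a 62% miss rate) for a 0.5-SD difference at 23 per arm. The documents do not support that. Nothing links section 9.4.5 to model choice, and the 62% concerns a true population difference, which randomization makes zero. Even if a baseline test did decide adjustment, type I error would not be inflated (about 0.043-0.045 in simulation at r = 0.5).

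**Conclusion.** The adjustment rule for the primary analysis is undefined, and an unconditional rule would be better at almost no cost. Under the stated assumptions with r = 0.5, routine baseline adjustment lowers variance by about 23-25% and adds about 10 points of power for an assumed 0.8-SD effect. Against follow-up-only, the gain runs from about 3 points at r = 0.3 to about 20 at r = 0.7. How much is lost depends on how baseline is coded, which the plan leaves open.

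The documents do not show that the planned test is invalid: any one of these models, fixed in advance, holds 5%. The 7% and 9-10% figures apply only if the model is chosen by its p-value, which the wording permits but does not prescribe. This is a change that should be made before the data are analysed, not a flaw that defeats the trial.

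**What to change.** In sections 9.4.1 and 9.4.2, delete *where necessary* for the baseline value. State that every primary model uses the baseline value of its outcome regardless of observed balance, and name one of two forms:

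- week-16 and week-24 values as outcomes, with arm, visit, arm-by-visit, the baseline value and its interaction with visit; or
- a constrained longitudinal model with baseline as an outcome and a common baseline mean in both arms. This targets the same contrast and keeps participants with missing baseline data, which suits the all-randomized population in section 9.3.

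Add to section 9.4.5 that the comparison is descriptive and will not decide adjustment. Apply the same rule to exploratory outcomes measured at baseline. The other covariates in the same sentence are equally open and should be named, although the figures above do not concern them.

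The cost is a sentence or two in the plan and one or two degrees of freedom per model. No new data or participants are needed.
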